#### Lactic Acid:

- Blood lactic acid levels [>4.0 mmol/L]) and decreased blood pH (>7.2 to <7.30) and no clinical symptoms of metabolic acidosis [nausea, vomiting, generalized muscle weakness, tachycardia, hypotension and rapid breathing] and normal potassium maintained in two consecutive laboratory assessments separated by >12 hours despite management as described in Section 4.1.11. To qualify as a DLT, the blood lactic acid levels [>4.0 mmol/L]) and decreased blood pH (<7.30) should be confirmed on arterial blood draws. Patients who develop pH between 7.30 - 7.35 while on therapy who are asymptomatic, and have other etiologies for metabolic acidosis ruled out, may be permitted to continue on treatment. These patients will have an increased monitoring of pH and lactate levels minimally at approximately 6 hours, 12 hours and 24 hours, until normalization of pH is established, so as to rule out any worsening acidosis. Patients with a baseline normal pH (>7.35) and no clinical evidence of progressive leukemia (defined by >50% blasts in the bone marrow or peripheral blood, white count >20K, requiring hydroxyurea to control WBC counts, or new extramedullary leukemia) who develop acidosis that fulfills the criteria for a DLT during the DLT window, should be considered a DLT.
- Blood lactic acid levels [>4.0 mmol/L]), decreased blood pH (<7.35 if the

baseline pre-therapy pH was >7.35 or blood pH <7.30 if the baseline pre-therapy pH was  $\leq$ 7.35), with bicarbonate >LLN and anion gap elevated, abnormal potassium and/or, in the opinion of the investigator, the subject is symptomatic for lactic acidosis [nausea, vomiting, generalized muscle weakness, tachycardia, hypotension and rapid breathing (Section 4.1.11, point 3). To qualify as a DLT, the blood lactic acid levels [>4.0 mmol/L]) and decreased blood pH <7.35 if the baseline pre-therapy pH was >7.35 or blood pH <7.30 if the baseline pre-therapy pH was  $\leq$ 7.35), should be confirmed on arterial blood draws.

 Second episode of blood lactic acid level > 4.0 mmol/L, confirmed as lactic acid level > 4.0 mmol/L on arterial blood, separated by >24 hours blood draw, in the presence of clinical symptoms attributable to lactic acidosis [nausea, vomiting, generalized muscle weakness, tachycardia, hypotension and rapid breathing]

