#### 4.1.11 Assessment of Elevated Lactic Acid Levels

Lactic acidosis is a potential mechanism-based side effect resulting from inhibition of mitochondrial oxidative phosphorylation by IACS-010759 and has been observed at high doses in preclinical studies. Peripheral venous or arterial lactate levels will be monitored during the trial as detailed in section 4.2 study flowchart. (Note: Venous or arterial blood may be used to monitor lactate and blood pH. Arterial blood lactate testing will also be used to confirm a potential DLT if an abnormal venous lactate level constitutes a DLT.)

A recent review by Kruse et al. [21] on the measurement of lactate concluded that peripheral venous lactate levels are highly correlated with arterial blood lactate levels. In the setting of elevated lactate, a complete physical exam and directed history will be performed to rule out other causes of elevated lactate levels (see appendix 9.1)

Subjects will have their lactic acid levels, blood pH as well as electrolytes including chloride and bicarbonate (reported as total CO2) levels measured according to section 4.2. Subjects with lactate levels >4 mmol/L and pH <7.30 and symptoms attributable to lactic acidosis [nausea, vomiting, generalized muscle weakness, tachycardia, hypotension and rapid breathing] will be hospitalized for monitoring of lactate levels and pH, electrolytes and symptoms of lactic acidosis [nausea, vomiting, generalized muscle weakness, tachycardia, hypotension and rapid breathing] for a minimum of 24 hours. The lactic acid and blood pH levels will be assessed as follows:

1. If lactic acid is > ULN but below 4.0 mmol/L, pH >7.35 and subject is asymptomatic, treatment can be continued. Patients with pH between 7.30 - 7.35 who are asymptomatic, and have other etiologies for metabolic acidosis ruled out, may be permitted to continue on treatment. These patients will have an increased monitoring of pH and lactate levels minimally at 6 hours, 12 hours and 24 hours, until normalization of pH is established, so as to rule out any worsening acidosis. Patients with a baseline normal pH (>7.35) and no clinical evidence of progressive leukemia (defined by >50% blasts in the bone marrow or peripheral blood, white count >20K, requiring hydroxyurea to control WBC counts, or new extramedullary leukemia) who develop acidosis that fulfills the criteria for a DLT during the DLT window, should be considered a DLT.

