- 2. If lactic acid >ULN but below 4.0 mmol/L, and subject is symptomatic (nausea, vomiting, generalized muscle weakness, tachycardia, hypotension and rapid breathing), treatment should be interrupted as indicated and lactic acidosis workup performed.
- 3. If lactic acid is above 4.0 mmol/L, blood pH ≥7.35 and bicarbonate (reported as total CO2) is <LLN, potassium is normal and anion gap <14, and subject is asymptomatic, dosing should be interrupted. Lactic acid and blood pH and electrolytes should be reassessed within 12 hours on arterial and/or venous blood draw until the lactic acid level is <4.0 mmol/L. Once the lactic acid level is <4.0 mmol/L on arterial and/or venous draw, the subject can continue therapy at the discretion of the investigator.
- 4. If lactic acid is above 4.0 mmol/L, blood pH <7.35 if the baseline pre-therapy pH was >7.35 or blood pH <7.30 if the baseline pre-therapy pH was ≤7.35) and the bicarbonate (reported as total CO₂) is <LLN and anion gap is elevated, and/or the subject is symptomatic, this will be considered a DLT. Treatment should be interrupted and lactic acidosis workup performed (See Section 7.2.3).

Anion gap via venous blood collection can be calculated as follows: Anion Gap= [Na+] - [Cl-] - [total CO2]; normal range 4-14 mmol/L.

Anion gap via arterial blood collection can be calculated as follows: Anion Gap= [Na+] - [Cl-] - [HCO3-]; normal range 8-16 mEq/L.

Symptoms of lactic acidosis include nausea, vomiting, generalized muscle weakness, tachycardia, hypotension and rapid breathing. Subjects with clinical symptoms concerning for lactic acidosis should have an arterial blood gas assessment. Lactic acidosis is characterized by an elevated blood lactate concentration [>4.0 mmol/L]), decreased blood pH (<7.35), and electrolyte disturbances with an increased anion gap.

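### For some asymptomatic subjects with lactate above 4.0 mmol/L and low pH, sections 4.1.10 and 4.1.11 disagree on whether a DLT has occurred

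*Combined protocol and SAP*

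**What the plan says.** Section 4.1.10 defines DLT and lists three lactic acid bullets.

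- **Bullet 1:** lactate above 4.0 mmol/L, pH above 7.2 and below 7.30, no symptoms, and "normal potassium maintained in two consecutive laboratory assessments separated by >12 hours despite management as described in Section 4.1.11". The same bullet also says that asymptomatic patients at pH 7.30-7.35, with other causes of acidosis excluded, may stay on drug under closer monitoring.
- **Bullet 2:** lactate above 4.0 mmol/L, pH below 7.35 (baseline above 7.35) or below 7.30 (baseline 7.35 or lower), "with bicarbonate >LLN and anion gap elevated, abnormal potassium and/or, in the opinion of the investigator, the subject is symptomatic for lactic acidosis", confirmed on arterial blood. It refers the reader to section 4.1.11, point 3.
- **Bullet 3:** a second episode of lactate above 4.0 mmol/L with symptoms.

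Section 4.1.11 is the assessment section, but it also classifies. Point 4 has the same lactate and pH limits as bullet 2 and then says that if bicarbonate "is <LLN and anion gap is elevated, and/or the subject is symptomatic, this will be considered a DLT". Its own action is "Treatment should be interrupted and lactic acidosis workup performed". Point 3, the one bullet 2 cites, covers pH of at least 7.35 and low bicarbonate where "potassium is normal and anion gap <14, and subject is asymptomatic, dosing should be interrupted"; dosing may resume once lactate falls below 4.0 mmol/L, and no DLT is declared.

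Section 4.1.9 calls for permanent discontinuation after any DLT due to lactic acid.

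**The concern.** The two sections state operative DLT rules from the same starting point but differ on the direction of bicarbonate, on potassium and, through the cross-reference, on which case is meant. An asymptomatic subject can therefore be a DLT or not depending on which section the reader applies.

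This matters because section 4.1.11 names lactic acidosis as a potential mechanism-based effect, and DLTs are the primary endpoint. The classification feeds the 3+3 step, the MTD and the expansion boundary. It also decides treatment: a DLT leads to permanent discontinuation under 4.1.9, while the pH 7.30-7.35 sentence in 4.1.10 bullet 1 lets such a patient continue.

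**Working it through.** **Set-up.** Hold fixed: lactate above 4.0 mmol/L and qualifying pH confirmed on arterial blood, baseline pH above 7.35, current pH 7.30 to <7.35, no symptoms, first cycle, related to drug. Bullet 1 (pH below 7.30) and bullet 3 (symptoms) then cannot apply. Three yes/no items remain: bicarbonate low, gap raised, potassium abnormal. That gives 2 x 2 x 2 = 8 profiles.

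**Rules.** Point 4 is (low bicarbonate and raised gap) or symptoms. The punctuation of bullet 2 allows three readings:
- R1: (bicarbonate above LLN and raised gap and abnormal potassium) or symptoms
- R2: bicarbonate above LLN and raised gap and (abnormal potassium or symptoms)
- R3: (bicarbonate above LLN and raised gap) or abnormal potassium or symptoms

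Without symptoms, R1 and R2 coincide. The last two columns change the bicarbonate sign to below LLN and nothing else.

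| Bicarbonate | Gap | Potassium | Point 4 | R1/R2 printed | R3 printed | R1/R2 sign changed | R3 sign changed |
|---|---|---|---|---|---|---|---|
| low | raised | abnormal | DLT | no | DLT | DLT | DLT |
| low | raised | normal | DLT | no | no | no | DLT |
| low | not raised | abnormal | no | no | DLT | no | DLT |
| low | not raised | normal | no | no | no | no | no |
| not low | raised | abnormal | no | DLT | DLT | no | DLT |
| not low | raised | normal | no | no | DLT | no | no |
| not low | not raised | abnormal | no | no | DLT | no | DLT |
| not low | not raised | normal | no | no | no | no | no |
| **Conflicts with point 4** | | | | **3 of 8** | **5 of 8** | **1 of 8** | **3 of 8** |

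**The example (second row).** Point 4 makes it a DLT. Bullet 2 as printed does not under any reading, and with the sign changed it still does not under R1 or R2. The sentence in bullet 1 about patients with normal baseline pH "who develop acidosis that fulfills the criteria for a DLT during the DLT window, should be considered a DLT" refers back to the criteria and does not say which ones, so it does not settle the case.

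**Which sign is likely meant.** "Anion gap via arterial blood collection can be calculated as follows: Anion Gap= [Na+] - [Cl-] - [HCO3-]; normal range 8-16 mEq/L". At fixed sodium and chloride, a fall of d in bicarbonate raises the gap by d, so low bicarbonate is the natural partner of a raised gap. This supports below LLN but does not prove it. The table shows that the sign alone never removes all conflicts. One shared criterion gives 0 of 8.

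**Asymptomatic, pH above 7.2 and below 7.30.** Bullet 1 now applies, so add a fourth item, persistence beyond 12 hours (16 profiles). With the sign changed and potassium kept (R1/R2):
- bullet 1 covers 4 profiles (normal potassium, persistent)
- bullet 2 covers 2 (low bicarbonate, raised gap, abnormal potassium)
- total 4 + 2 = 6

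With potassium dropped, bullet 2 covers 4, one of them shared with bullet 1: 4 + 4 - 1 = 7. The added profile is low bicarbonate, raised gap, normal potassium, not persistent. Point 4 as printed already counts it.

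**What one disputed subject can do.** Under 4.1.7: 0/3 escalates while 1/3 enrols three more; 1/3 enrols three more while 2/3 exceeds the MTD; 1/6 escalates while 2/6 exceeds the MTD. In the expansion phase, the prior beta(0.4, 1.6) and the 0.80 limit reproduce the Table 3 boundaries of 4 in 12 and 6 in 18:
- 3 of 12: beta(0.4 + 3, 1.6 + 9) = beta(3.4, 10.6), Pr(P_T > 0.20) = 0.608, continue
- 4 of 12: beta(0.4 + 4, 1.6 + 8) = beta(4.4, 9.6), Pr(P_T > 0.20) = 0.821, stop

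**The case against.** The printed sign in bullet 2 may be a typing or text-extraction error. Point 4 states plainly that its case is a DLT, and nothing says 4.1.10 overrides it. DLT calls also need a judgement on clinical significance and relatedness, under Safety Monitoring Committee (SMC) review at one site. The profile counts say nothing about how often such subjects occur, and any single disputed DLT would have the 3+3 effects shown.

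Most of this stands and limits the size of the point. It does not remove it: with the sign changed, the potassium mismatch and the wrong cross-reference remain.

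The direction of repair is also open. The log for Amendment 4 describes superseded text, but as history it shows that asymptomatic pH 7.30-7.35 was handled on purpose, citing variable and typically lower pH in leukemia, SMC advice and FDA feedback. Not counting the example may be what was intended.

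Two stronger readings are tempting. A reader might infer that DLTs will be under-counted and the MTD set too high. The documents support this only if 4.1.10 governs over point 4; if both sections are applied as a union, the example is counted and nothing is lost. A reader might also take the permission to continue as irrelevant here, because 4.1.11 point 1 opens with "If lactic acid is > ULN but below 4.0 mmol/L, pH >7.35 and subject is asymptomatic, treatment can be continued". But the same permission stands in 4.1.10 bullet 1, which opens at lactate above 4.0 mmol/L, so it does bear on the example.

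**Conclusion.** The point holds for some asymptomatic subjects, not all: under R1 and R2, 5 of the 8 profiles agree. For the rest, the protocol gives two DLT answers and, in the example, two treatment answers: permanent discontinuation through point 4 and 4.1.9, or possible continuation through bullet 1. The cross-reference to point 3 is wrong under every reading.

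The size is 3 of 8 logical profiles in conflict as printed (5 of 8 under R3), and 1 of 8 (3 of 8 under R3) with only the sign changed. These are not frequencies; bicarbonate and gap are linked, and the event rate is unknown. No change in escalation probability is claimed. The statement is limited to the lactic acid bullets, since the general grade 3 and 4 criteria could count an event on its CTCAE grade, which the documents do not reproduce. Symptomatic subjects agree if symptoms suffice alone in both sections, which the punctuation leaves unclear.

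**What to change.** In one amendment:

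1. In 4.1.10 bullet 2, change bicarbonate to below LLN, point the cross-reference to 4.1.11 point 4, and state that symptoms alone suffice.
2. Use one identical criterion in both sections. A workable form is lactate above 4.0 mmol/L; the existing baseline-dependent pH limits; and either low bicarbonate (total CO2) with raised gap, or symptoms; confirmed on arterial blood.
3. Reconcile the pH 7.30-7.35 permission wherever it appears (4.1.10 bullet 1 and 4.1.11 point 1). Either limit it to subjects who do not meet the criterion, for example lactate of 4.0 mmol/L or less, or no low bicarbonate with raised gap. Or, if the sponsor, SMC and FDA intend asymptomatic subjects in this range not to be DLTs, say so in point 4 and carry the same exemption into bullet 2. Without this step, a continuation rule would sit beside the discontinuation rule of 4.1.9.
4. Have the sponsor and SMC decide whether a potassium term applies, and which bullet governs asymptomatic, normal-potassium subjects at pH below 7.30. Dropping potassium makes one more profile there a DLT under 4.1.10 without the 12-hour persistence test. These are clinical choices; whichever is made must read the same in both sections.
5. Re-adjudicate first-cycle events with lactate above 4.0 mmol/L and low pH.

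The cost is wording, these decisions and the re-adjudication; no new data are needed. Earlier changes to this definition went through the SMC and FDA, so the same review should be expected.

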#### 4.1.11 Assessment of Elevated Lactic Acid Levels

Lactic acidosis is a potential mechanism-based side effect resulting from inhibition of mitochondrial oxidative phosphorylation by IACS-010759 and has been observed at high doses in preclinical studies. Peripheral venous or arterial lactate levels will be monitored during the trial as detailed in section 4.2 study flowchart. (Note: Venous or arterial blood may be used to monitor lactate and blood pH. Arterial blood lactate testing will also be used to confirm a potential DLT if an abnormal venous lactate level constitutes a DLT.)

A recent review by Kruse et al. [21] on the measurement of lactate concluded that peripheral venous lactate levels are highly correlated with arterial blood lactate levels. In the setting of elevated lactate, a complete physical exam and directed history will be performed to rule out other causes of elevated lactate levels (see appendix 9.1)

Subjects will have their lactic acid levels, blood pH as well as electrolytes including chloride and bicarbonate (reported as total CO2) levels measured according to section 4.2. Subjects with lactate levels >4 mmol/L and pH <7.30 and symptoms attributable to lactic acidosis [nausea, vomiting, generalized muscle weakness, tachycardia, hypotension and rapid breathing] will be hospitalized for monitoring of lactate levels and pH, electrolytes and symptoms of lactic acidosis [nausea, vomiting, generalized muscle weakness, tachycardia, hypotension and rapid breathing] for a minimum of 24 hours. The lactic acid and blood pH levels will be assessed as follows:

1. If lactic acid is > ULN but below 4.0 mmol/L, pH >7.35 and subject is asymptomatic, treatment can be continued. Patients with pH between 7.30 - 7.35 who are asymptomatic, and have other etiologies for metabolic acidosis ruled out, may be permitted to continue on treatment. These patients will have an increased monitoring of pH and lactate levels minimally at 6 hours, 12 hours and 24 hours, until normalization of pH is established, so as to rule out any worsening acidosis. Patients with a baseline normal pH (>7.35) and no clinical evidence of progressive leukemia (defined by >50% blasts in the bone marrow or peripheral blood, white count >20K, requiring hydroxyurea to control WBC counts, or new extramedullary leukemia) who develop acidosis that fulfills the criteria for a DLT during the DLT window, should be considered a DLT.

- 2. If lactic acid >ULN but below 4.0 mmol/L, and subject is symptomatic (nausea, vomiting, generalized muscle weakness, tachycardia, hypotension and rapid breathing), treatment should be interrupted as indicated and lactic acidosis workup performed.
- 3. If lactic acid is above 4.0 mmol/L, blood pH ≥7.35 and bicarbonate (reported as total CO2) is <LLN, potassium is normal and anion gap <14, and subject is asymptomatic, dosing should be interrupted. Lactic acid and blood pH and electrolytes should be reassessed within 12 hours on arterial and/or venous blood draw until the lactic acid level is <4.0 mmol/L. Once the lactic acid level is <4.0 mmol/L on arterial and/or venous draw, the subject can continue therapy at the discretion of the investigator.
- 4. If lactic acid is above 4.0 mmol/L, blood pH <7.35 if the baseline pre-therapy pH was >7.35 or blood pH <7.30 if the baseline pre-therapy pH was ≤7.35) and the bicarbonate (reported as total CO₂) is <LLN and anion gap is elevated, and/or the subject is symptomatic, this will be considered a DLT. Treatment should be interrupted and lactic acidosis workup performed (See Section 7.2.3).

Anion gap via venous blood collection can be calculated as follows: Anion Gap= [Na+] - [Cl-] - [total CO2]; normal range 4-14 mmol/L.

Anion gap via arterial blood collection can be calculated as follows: Anion Gap= [Na+] - [Cl-] - [HCO3-]; normal range 8-16 mEq/L.

Symptoms of lactic acidosis include nausea, vomiting, generalized muscle weakness, tachycardia, hypotension and rapid breathing. Subjects with clinical symptoms concerning for lactic acidosis should have an arterial blood gas assessment. Lactic acidosis is characterized by an elevated blood lactate concentration [>4.0 mmol/L]), decreased blood pH (<7.35), and electrolyte disturbances with an increased anion gap.

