#### 4.1.9 Dosing Adjustments, Delays and Discontinuations

IACS-010759 dose reduction/interruption/discontinuation decisions should be based on the CTCAE version 4.03 of the toxicity and according to the guidelines shown below. If toxicity is not covered in the table, doses may be reduced or held at the discretion of the investigator for the subject's safety. Additional PK, blood pH and lactate testing will be performed following a dose reduction or resumption of dosing following a dose interruption, as described in Section 4.2. IACS-010759 should be permanently discontinued in any subject that develops DLT due to lactic acid.

If a dose interruption occurs at the end of a cycle, the next cycle will be delayed and start on the first day of dosing of the next cycle. Dose interruptions which occur during a cycle will not change the study days during the cycle.

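### 4.1.11 point 3 directs a hold and 12-hour recheck for an asymptomatic subject with lactate >4.0, normal pH and low bicarbonate, but not if the anion gap is elevated or potassium is abnormal

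*Combined protocol and SAP*

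**What the plan says.** Section 4.1.11 names lactic acidosis as a potential mechanism-based effect and gives four numbered responses to raised lactate.

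- **Points 1 and 2** set actions for lactate above ULN but below 4.0 mmol/L.
- **Point 3** takes lactate above 4.0 mmol/L, pH at or above 7.35 and bicarbonate below LLN, then adds further conditions: "potassium is normal and anion gap <14, and subject is asymptomatic, dosing should be interrupted". Lactate, pH and electrolytes "should be reassessed within 12 hours on arterial and/or venous blood draw" until lactate is below 4.0. The subject may then continue at the investigator's discretion.
- **Point 4** takes lactate above 4.0 with a lowered pH, low bicarbonate and elevated gap, and/or symptoms: "this will be considered a DLT. Treatment should be interrupted and lactic acidosis workup performed".

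The same section gives the normal anion gap as 4-14 mmol/L on venous blood and, on arterial blood, "normal range 8-16 mEq/L". Its description of lactic acidosis combines lactate above 4.0, pH below 7.35 and "electrolyte disturbances with an increased anion gap". The second lactic-acid criterion in 4.1.10 includes "anion gap elevated, abnormal potassium and/or, in the opinion of the investigator", the subject is symptomatic.

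Two general provisions also apply. For any elevated lactate, "a complete physical exam and directed history will be performed to rule out other causes of elevated lactate levels". Under 4.1.9, for toxicity not covered in its table, "doses may be reduced or held at the discretion of the investigator".

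**The concern.** The conditions in point 3 are joined by 'and', so normal potassium and a gap below 14 are requirements for the hold. Take a subject who qualifies and change one finding for the worse, by raising the gap above its normal range or making potassium abnormal. The directed interruption and the 12-hour recheck then no longer apply. Read as written, the plan handles a subject closer to its own picture of lactic acidosis less strictly than a milder one, for the toxicity it singles out as mechanism-based. At stake is the prompt detection of a subject moving from compensated to overt acidosis while dosing continues.

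**Working it through.** The plan gives no figure to reproduce. The check is whether any other rule catches the subject.

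**1. Rules at lactate >4.0, pH >=7.35, asymptomatic**

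| Rule | What it needs | Applies? |
|---|---|---|
| 4.1.11 points 1, 2 | lactate below 4.0 | No (see note) |
| 4.1.11 point 3 | bicarbonate <LLN, potassium normal, gap <14 | Only with all three |
| 4.1.11 point 4 | lowered pH, or symptoms if the 'and/or' is a stand-alone limb | No, on either reading |
| 4.1.10, first lactic criterion | pH below 7.30 | No |
| 4.1.10, second | lowered pH, confirmed on arterial blood | No |
| 4.1.10, third | second episode with symptoms | No |
| 4.1.11 hospitalization | pH below 7.30 and symptoms | No |
| 4.1.9 Table 5 | clinically significant drug-related event; no dose reduction at grade 1 or 2 | Perhaps, for a higher-grade potassium event; no lactate or pH recheck |

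Note: at pH exactly 7.35, the sentence in point 1 on pH 7.30-7.35 could be read as allowing treatment to continue.

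**2. Low-bicarbonate combinations**

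Potassium (normal, abnormal) x gap (<14, >=14) = 2 x 2 = 4.

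| Potassium | Gap | Directed hold and 12-hour recheck |
|---|---|---|
| Normal | <14 | Yes, point 3 |
| Normal | >=14 | None |
| Abnormal | <14 | None |
| Abnormal | >=14 | None |

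One of four is covered.

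**3. What the 14 cut-off does**

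A gap of exactly 14 is inside the venous range (4-14), and 14-16 is inside the arterial range (8-16). With normal potassium, such subjects are uncovered but no worse than the covered profile. The gap is elevated only above 14 (venous) or above 16 (arterial).

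**4. Bicarbonate not below LLN**

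Point 3 requires low bicarbonate, so it covers none of these subjects, even with an elevated gap or abnormal potassium. Classify by bicarbonate (low or not), gap (elevated for sample type or not) and potassium (normal or abnormal): 2 x 2 x 2 = 8 profiles. Point 3 now reaches part of one: low bicarbonate, normal potassium, gap not elevated and below 14. A trigger on any of the three abnormalities reaches 8 - 1 = 7 and leaves out only isolated raised lactate.

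**5. Cost in missed doses, cohorts 5 and 6**

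Doses are from Table 2. I take days 8-21 as two weeks at three doses, so 6 maintenance doses in cycle 1.

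- Cohort 5: 5 x 2.5 + 6 x 1.5 = 21.5 mg; 75% = 16.125 mg.
- Cohort 6: 5 x 3 + 6 x 2 = 27 mg; 75% = 20.25 mg.

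| Missed cycle 1 doses | Lowest share left | Highest share left |
|---|---|---|
| 1 | 19/21.5 = 88.4% | 20/21.5 = 93.0% |
| 2 | 16.5/21.5 = 76.7% | 18.5/21.5 = 86.0% |
| 3 | 14/21.5 = 65.1% | 17/21.5 = 79.1% |

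Counted in doses (11 planned), the shares are 10/11 = 90.9%, 9/11 = 81.8% and 8/11 = 72.7%. One or two missed doses keep a subject above the 75% needed for MTD evaluability (4.1.13). Three may not.

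**The case against.** The strongest reply is that these subjects are not neglected. The exam and directed history apply to every elevated lactate, the investigator may hold the dose, and unscheduled lactate and pH draws are allowed. In cohorts 5-7, lactate and pH are scheduled on cycle 1 days 1, 2, 4, 5, 8, 12, 15, 17 and 21. A reader might infer that subjects with the omitted profiles go unmonitored; the documents do not support that. What they lack is a directed hold and a recheck within 12 hours, which the milder profile receives and none of these provisions supplies. Scheduled sampling also thins out: in cycle 3 it falls on study days 43 and 63, 20 days apart.

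Second, the protocol's own markers are not gap and potassium alone. Its description of lactic acidosis and the second criterion in 4.1.10 both require a lowered pH, and that criterion specifies bicarbonate above LLN, not below. This stands. It rules out calling the omitted profiles lactic acidosis or missed DLTs. It also means that 4.1.10 is thin support for low-bicarbonate profiles in particular, and argues for a trigger that does not depend on bicarbonate.

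Third, a reader might infer that all three uncovered low-bicarbonate combinations are worse than the covered one. Step 3 shows that this goes too far for gaps within the normal range. The protocol also gives neither direction nor size for abnormal potassium.

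Finally, raised lactate is an anticipated pharmacodynamic effect (8.1.3), so a hold for every value above 4.0 would be excessive. That is accepted, and the fix leaves isolated raised lactate to discretion.

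**Conclusion.** The point holds as a gap in directed safety management. An asymptomatic subject with lactate above 4.0, pH at or above 7.35 and low bicarbonate falls outside point 3 once the gap is elevated or potassium is abnormal, and no other lactate rule directs a hold or a recheck. Point 3 covers one of four low-bicarbonate combinations; part of the remainder is uncovered rather than worse.

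This rests on reading 'and' in point 3 literally and on the subject being asymptomatic. Symptomatic subjects at normal pH are caught only if symptoms are a stand-alone limb of point 4. The documents give no frequency, so the number of subjects affected is unknown.

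A reader might infer that dose finding is compromised. It is not: DLT definitions, 3+3 decision rules and Table 3 boundaries do not depend on point 3. The change should be made because the rule concerns the named mechanism-based toxicity and the correction is one of wording.

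**What to change.** Reword 4.1.11 point 3 so that interruption and reassessment within 12 hours apply to every asymptomatic subject with lactate above 4.0 mmol/L and pH at or above 7.35 who has any of:

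- bicarbonate below LLN;
- anion gap above the normal range for the sample type (above 14 venous, above 16 arterial);
- abnormal potassium.

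Point 3 now lets a subject restart on lactate alone. Keep the requirement of lactate below 4.0, and add that the investigator reviews potassium and anion gap before restart. Raised lactate with normal bicarbonate, gap and potassium may stay at the investigator's discretion.

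The cost is a wording amendment and more interruptions. Their number and length cannot be estimated: point 3 sets no limit on a hold, and 3.1 reports accumulation with falling clearance. Repeated holds in cycle 1 could take a subject below 75% of planned drug and require replacement. Missed doses could also count toward the 80% planned-dose pause rule in 4.1.7. Sample size does not change.
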